from the first day of study treatment through the end of study. Safety data will include local and systemic signs and symptoms, laboratory measures of safety/toxicity, and all adverse and serious adverse events.

Other Endpoints:

1. Change in the frequency of HIV infection per million resting CD4⁺ T cells (RCI) from baseline to post-treatment with VRC07-523LS combined with VOR.
2. Change in HIV RNA expression within resting CD4⁺ T cells in HIV-infected participants on stable ART from baseline to after the receipt of two series of VRC07-523LS given with VOR.
3. Change in HIV-1 RNA by low level viremia assay from baseline to post-treatment with VRC07-523LS and VOR.
4. Change in the chromosomally integrated viral reservoir as measured by quantitative-polymerase chain reaction (Q-PCR) from baseline to post-treatment with VRC07-523LS and VOR.
5. Change in frequency of viral envelope sequences detected in plasma or cells that are not recognized by VRC07-523LS from baseline to post-treatment with VRC07-523LS and VOR.
6. Pharmacokinetics of VRC07-523LS in combination with VOR.

Population: Healthy men and women of any race with HIV-1 infection, ages 18 through 64, suppressed on ART therapy for ≥ 24 months.

Phase: Phase I

Description of Sites/Facilities Enrolling Participants: This study will be conducted at a single site, The University of North Carolina (UNC) at Chapel Hill (USA). The study will enroll up to 12 participants.

Description of Study Intervention: Participants will receive two treatment interventions (series):

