9.2 SAMPLE SIZE DETERMINATION

We will enroll up to 12 fully evaluable participants (who receive two cycles of VRC07-523LS and VOR) to examine the effect of adding VOR and VRC07-523LS to ART on persistent replication-competent HIV within resting CD4+ T cells.

Any participant who does not complete both series of VRC07-523LS and VOR and the leukapheresis in Step 4 for reasons other than a grade 3 or higher AE will be replaced, to ensure up to 12 evaluable participants for safety.

Since the trial will be stopped if two participants experience a study treatment-related toxicity of Grade 3 or higher, the criterion for safety is grade 3 or higher toxicity in no more than 1 of 12 participants in the study.

For n=12 participants, if there are no primary AEs, then the exact 95% 1-sided upper confidence limit (UCL) for the true AE rate will be 0.22. Thus, if no AEs are observed, one can confidently rule out event rates greater than 22%.

All other analyses are therefore equally exploratory.

Because a focus of the study is on safety and potential AEs, accrual will be staggered such that enrollment and treatment administration will include a maximum of 1 participant per week.

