9.4.3 ANALYSIS OF THE OTHER ENDPOINT(S)

Other Activity Endpoints:

- **Change in the frequency of HIV infection per million resting CD4⁺T cells (RCI) from baseline to after treatment with VRC07-523LS and VOR**

We will analyze pre-VOR/VRC07-523LS and post- VOR/VRC07-523LS frequency of HIV infection per million resting CD4⁺T cells using a non-parametric 2-sided sign test (supplemented by longitudinal regression modeling to estimate the magnitude of changes) to determine whether or not a significant decrease of IUPM is observed. With 12 participants, there will be 80% power to reject H₀ (change expected with ART alone) in favor of H_A (greater change than expected with ART) if the true probability of observing a decrease in IUPM in a participant after VOR/VRC07-523LS is 0.93.

This is based on a 2-sided alpha = 0.05 and the assumption that observed HIV infection frequency would decrease with probability 0.54 on ART alone after 6 months without intervention, based on the decay of IUPM seen on ART alone [Crooks 2015, Siliciano 2003].

In addition to summarizing the number and proportion of participants who show decrease in IUPM after VOR/VRC07-523LS, we will describe the magnitude of the changes in decrease in IUPM after VOR/VRC07-523LS via the median fold-change and corresponding 95% confidence interval. We will also summarize the proportion of participants with >6-fold decreases; this magnitude change is rarely seen in participants on stable ART [9].

Other Endpoints: Activity

- **HIV-1 RNA by low level viremia assay measurement at baseline and after treatment with VRC07-523LS and VOR**

The virologic analysis will include estimation of the low level viremia levels at pre-treatment (screening and entry) and separately at post-treatment. We assume that the probability would be 0.10 (10%) for a baseline (pre-entry, entry) detectable low level viremia ≥ 1 copy. The assumption that 10% of participants with a quantifiable low level viremia at screening will have low level viremia assay below the limit of detection at a pre-treatment measure is an estimate based on data from A5244 in which 6 of 50 (12%) enrolled participants had undetectable low

level of viremia at pre-entry and 5 of 51 (10%) at entry after having a screening low level of viremia ≥ 1 copy (59).

Other Exploratory Analyses:

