- Following VOR/VRC07-523LS we will also explore whether there is a *depletion* of rc-RNA using the same statistical tests in the reverse (compare baseline rc-RNA to after two cycles of VOR/VRC07-523LS).
- To assess these within each individual participant (n of 1 analyses), we will use the non-parametric 2-sided Wilcoxon rank sum test to determine whether or not a statistically significant change in rc-RNA expression is observed, comparing rc-RNA levels measured in each of 24-36 replicate pools of 1 million resting CD4⁺ cells. Pools with undetectable RNA will be considered as 0 copies and analyzed as the lowest rank in this rank-based statistical test.

The pre-VOR rc-RNA expression will be determined as the median RNA copies over the individual pools of one million participant cells tested prior to VOR (setting undetectable RNA pools as 0 copies), and the post-VOR RNA expression level will be similarly determined. Changes in RNA expression will be evaluated by the exact sign test and the proportion of participants with increases versus decreases. Summaries of the magnitude of changes will be examined in terms of median fold-changes.

- We will also explore changes in the chromosomally integrated viral reservoir as measured by Q-PCR from baseline to post VOR/VRC07-523LS.
- We will also explore the change in frequency of viral envelope sequences detected in plasma or cells that are not recognized by VRC07-523LS from baseline to post VOR/VRC07-523LS.
- A 0.05 significance level will be used throughout, with no adjustment for multiple testing given the proof of concept nature of this study. Emphasis will be put on estimation with corresponding 95% confidence intervals to evaluate the scientific and biologic effect size. Individual-level data will be visualized in plots. Given the small sample size, exploratory analyses will have limited or no statistical power and findings should be interpreted with caution and assessed in a subsequent, larger study if the combined treatment is found to be safe and potentially efficacious. If the study is stopped at n=12 participants, statistical analyses will be limited to descriptive summaries and n of 1 analyses within each participant.

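### Section 9.4.3 plans group sign tests with 12 participants, then limits a study stopped at 12, its planned maximum, to descriptive and n-of-1 analyses

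*Combined protocol and SAP*

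**What the plan says.** Section 1.1 sets the size of the study: "The study will enroll up to 12 participants". Section 9.2 says "We will enroll up to 12 fully evaluable participants" and provides for replacement of most non-completers so as to hold that number. No stage or expansion beyond 12 is described.

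Section 9.4.3, under Other Activity Endpoints, compares IUPM before and after treatment with a 2-sided sign test across participants, supported by longitudinal regression to estimate the size of the change. It states: "With 12 participants, there will be 80% power to reject" the null hypothesis. The inputs are a 0.54 probability of a decrease on ART alone, 0.93 under the alternative, and 2-sided alpha 0.05.

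Under Other Exploratory Analyses, the section describes within-participant (n-of-1) Wilcoxon rank sum tests on replicate pools of resting cells. It then adds a group test on rc-RNA: "Changes in RNA expression will be evaluated by the exact sign test". A 0.05 level applies to all analyses, without multiplicity adjustment.

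The last sentence of the section reads: "If the study is stopped at n=12 participants, statistical analyses will be limited to descriptive summaries and n of 1 analyses within each participant".

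**The concern.** A sign test across participants is neither a descriptive summary nor an n-of-1 analysis; the section uses the latter term for the within-participant rank sum tests. If stopping at 12 means reaching planned enrolment, the last sentence removes tests that the same section has just specified, one of them with a power calculation for that very sample size.

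An analyst cannot comply with both parts. Running the sign tests contradicts the last sentence, and omitting them contradicts the earlier text. In an open-label, single-arm study the choice could be made after the results are known. The IUPM test carries weight in the protocol's own argument: section 8.1 (Resting CD4 T Cell Infection) treats a statistically significant decline in the frequency of resting-cell infection as definitive evidence that the reservoir has shrunk.

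**Working it through.** **Step 1. Is the 80% figure really a group-test calculation for 12 participants?**

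Inputs, all from section 9.4.3: n = 12, null probability 0.54, alternative 0.93, 2-sided alpha 0.05. Let X be the number of participants whose IUPM decreases, binomial (12, p). An equal-tailed exact test allows at most 0.025 in each tail.

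- Upper tail at p = 0.54: P(X ≥ 11) = 12 × 0.54^11 × 0.46 + 0.54^12 = 0.0069. P(X ≥ 10) = 0.0363, above 0.025. The upper critical value is 11.
- Lower tail at p = 0.54: P(X ≤ 2) = 0.0095. P(X ≤ 3) = 0.0415, above 0.025. The lower critical value is 2.
- Total size: 0.0069 + 0.0095 = 0.0164.
- Power at p = 0.93: P(X ≥ 11) = 12 × 0.93^11 × 0.07 + 0.93^12 = 0.3781 + 0.4186 = 0.797. The lower tail adds a negligible amount.

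This matches the stated 80%. The alternatives tried do not: rejecting at 10 or more (the one-sided 0.05 rule, and also the minimum-likelihood 2-sided rule) gives 0.953, and the normal approximation gives 0.929. The power statement is therefore specific to an exact test across 12 participants.

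**Step 2. Is the rc-RNA sign test workable at 12?**

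The plan gives no null probability. Assuming 0.5:

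- 10 of 12 in the same direction: 2 × P(X ≥ 10) = 0.039, which rejects at 0.05.
- 9 of 12: 2 × P(X ≥ 9) = 0.146, which does not.

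So neither test needs to be dropped at 12 because it cannot reach significance.

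**Step 3. What does the last sentence remove, under each reading?**

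| Reading | Removed at n = 12 |
|---|---|
| Literal: all statistical analyses, 12 being full enrolment | IUPM sign test, rc-RNA sign test, and the regression unless it is classed as descriptive |
| Only analyses under Other Exploratory Analyses | rc-RNA sign test |
| Only after a toxicity halt | The same tests, but only if the halt falls at exactly 12; no rule for a halt at a smaller number |

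On the first two readings at least one planned group test is removed at the sample size for which it was planned. The third needs a condition that the sentence does not contain. It also puts the restriction at the largest possible sample while leaving smaller ones without one.

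**The case against.** The strongest defence concerns scope. The sentence closes a list under Other Exploratory Analyses and follows a remark about the limited power of exploratory work, whereas the IUPM test sits under a separate heading. Read by placement, it does not reach IUPM. That is a fair reading, but not a secure one: the sentence refers to statistical analyses without qualification, and section 9.2 says of everything beyond the primary endpoint: "All other analyses are therefore equally exploratory". Even if accepted, it leaves the rc-RNA contradiction in place.

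Second, section 9.2 does use the word stopped for a halt after two participants with related Grade 3 or higher toxicity (section 9.4.2 calls the same event a pause). The halt reading therefore has some textual support, though the sentence gives no cause.

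Third, 12 enrolled need not mean 12 evaluable. Section 1.1 caps participants, section 9.2 speaks of evaluable ones, and enrolment at Visit 2 precedes the IUPM advancement criterion. This ambiguity is real. It adds to the need for a clear definition and does not supply one.

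Fourth, the consequence is limited. The plan separately commits to reporting the number and proportion with a decrease in IUPM and the median fold-change with its confidence interval. With the IUPM null fixed at 0.54, anyone can recover the sign-test p-value from the counts. This lowers the stakes for IUPM. It helps less for rc-RNA, where no null is stated, and it does not settle which tests the report must present.

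It is also fair to say that the regression, whose stated purpose is estimation, might count as descriptive.

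**Conclusion.** The concern holds. Section 9.4.3 contradicts itself at the planned sample size. On the literal reading two named sign tests are barred, with the regression in doubt; on the narrower reading by heading, one is (rc-RNA). The IUPM test is the only activity test with a stated power, and that power (79.7% recomputed) belongs to the same 12 participants at which the last sentence would rule the test out.

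The conclusion takes 12 as the planned maximum, as sections 1.1 and 9.2 state. The rc-RNA rejection rule assumes a null of 0.5, but the contradiction does not depend on it. Section 10.3 records that version 3.0 raised enrolment to 12, so the sentence may survive from an earlier design; the documents do not confirm this.

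The matter should be fixed, but it is confined to exploratory endpoints. The primary safety analysis is untouched.

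**What to change.** Delete the last sentence of section 9.4.3, or limit it to early termination. Suggested wording: *If the study is terminated early with fewer than [number below 12, chosen by the sponsor] participants having paired baseline and post-treatment results, statistical analyses will be limited to descriptive summaries and n of 1 analyses.* Then state that the IUPM sign test, its supporting regression and the rc-RNA sign test are performed at n = 12. Counting participants with paired results also removes the doubt about enrolled versus evaluable numbers.

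If the sponsor does intend a purely descriptive analysis at 12, the consistent alternative is to keep the restriction and withdraw the group tests and the power statement. The deliberate n = 12 power calculation points to the first option.

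Either change costs one or two sentences of analysis-plan wording, with no new data, participants or procedures. It should be made before the post-treatment results are analysed.

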9.4.4 SAFETY ANALYSES

For the safety endpoint, we will describe all study treatment-related AEs through the end of study approximately 20 weeks after getting their first infusion at Day 0. AEs will be coded to the Medical Dictionary for Regulatory Activities (MedDRA). Events prior to treatment (e.g., due to study-related procedure) will be listed separately in an appendix to the final clinical study report. The following tables of AE data will be created to summarize the number and percent of participants who experience at least one event of each of the following types:

- All AEs
- Drug-related AEs by severity grade
- AEs by severity grade

- All SAEs (this may be a listing if there are few events)
- Drug-related SAEs
- Fatal AEs (this may be a listing if there are few events)
- AEs that result in study discontinuation
- AEs that lead to withdrawal of study drug
- AEs categorized as AESI and/or IREs
- AEs with severity grade 3 or greater
- Drug-related AEs with severity grade 3 or greater

All of these tables will display the number and percent of participants that experience the given event and will display events by System Organ Class (SOC) and Preferred Term (PT). Events will be displayed alphabetically for SOC and in descending order of overall PT incidence within each SOC.

9.4.5 TABULATION OF INDIVIDUAL PARTICIPANT DATA

Individual participant data will be listed by measure and time point.

10 SUPPORTING DOCUMENTATION AND OPERATIONAL CONSIDERATIONS

10.1 REGULATORY, ETHICAL, AND STUDY OVERSIGHT CONSIDERATIONS

10.1.1 INFORMED CONSENT PROCESS

10.1.1.1 CONSENT AND OTHER INFORMATIONAL DOCUMENTS PROVIDED TO PARTICIPANTS

Consent forms describing in detail the study intervention, study procedures, and risks are given to the participant and written documentation of informed consent is required prior to starting intervention/administering study intervention.

10.1.1.2 CONSENT PROCEDURES AND DOCUMENTATION

Informed consent is a process that is initiated prior to the individual's agreeing to participate in the study and continues throughout the individual's study participation. The consent forms are UNC IRB - approved and the participant will be asked to read and review the document. The study investigator (or designee) and/or study coordinator will explain the research study to the participant and answer any questions that may arise. A verbal explanation will be provided in terms suited to the participant's comprehension of the purposes, procedures, and potential risks of the study and of their rights as research participants. Participants will have the opportunity to carefully review the written consent form and ask questions prior to signing. The participants are provided the opportunity to discuss the study with their family, primary care provider, or significant other or to just think about the study and its requirements prior to agreeing to participate. The participant signs the informed consent document prior to any procedures being done specifically for the study. Participants are informed that participation is voluntary and that they may withdraw from the study at any time, without prejudice. A copy of the informed consent document will be given to the participants.

The informed consent process will be conducted and documented in the source document, and the consent form signed, before the participant undergoes any study-specific procedures. The study PI (or designee) or the research coordinator will inform participants that the quality of their medical care will not be adversely affected if they decline to participate in this study, thus emphasizing the protection of the rights and welfare of the participants.

10.1.2 STUDY DISCONTINUATION AND CLOSURE

This study may be temporarily suspended or prematurely terminated if there is sufficient reasonable cause. Written notification, documenting the reason for study suspension or termination, will be provided to the study participants, funding agency (NIH), the FDA (IND), the VRC (VRC07-523LS), Merck (Vorinostat) and UNC IRB. If the study is prematurely terminated or suspended, the study PI (or designee) will promptly inform study participants, the UNC IRB, and DAIDS and will provide the reason(s) for the termination or suspension. Study participants will be contacted, as applicable, and be informed of changes to the study visit schedule.

Circumstances that may warrant termination or suspension include, but are not limited to:

- Determination of unexpected, significant, or unacceptable risk to participants
- Demonstration of efficacy that would warrant stopping
- Insufficient compliance to protocol requirements
- Data that are not sufficiently complete and/or evaluable
- Determination that the primary endpoint has been met
- Determination of futility

Study may resume once concerns about safety, protocol compliance, and data quality are addressed, and satisfy DAIDS, UNC IRB, and/or FDA.

10.1.3 CONFIDENTIALITY AND PRIVACY

Participant confidentiality and privacy is strictly held in trust by the participating investigators, their staff, and the sponsor(s) and their interventions. This confidentiality is extended to cover testing of biological samples and genetic tests in addition to the clinical information relating to participants. Therefore, the study protocol, documentation, data, and all other information generated will be held in strict confidence. No information concerning the study or the data will be released to any unauthorized third party without prior written approval of the sponsor.

All research activities will be conducted in as private a setting as possible.

The study monitor, other authorized representatives of the sponsor, representatives of the UNC IRB, regulatory agencies or pharmaceutical company supplying study product may inspect all documents and records required to be maintained by the study PI, including but not limited to, medical records and pharmacy records for the participants in this study. The clinical study site will permit access to such records.

The study participants' contact information will be securely stored at the clinical study site for internal use during the study. At the end of the study, all records will continue to be kept in a secure location for as long a period as dictated by the reviewing IRB, Institutional policies, or sponsor requirements.

Study participant research data, which is for purposes of statistical analysis and scientific reporting, will be stored at the UNC HIV Cure Center. This will not include the participants' contact or identifying information. Rather, individual participants and their research data will be identified by a unique study identification number. The study data entry and study management systems used by the clinical staff of the UNC HIV Cure Center and by research staff will be secured and password protected. At the end of the study, all study databases will be de-identified and archived.

Certificate of Confidentiality

To further protect the privacy of study participants, a Certificate of Confidentiality will be issued by the National Institutes of Health (NIH). This certificate protects identifiable research information from forced disclosure. It allows the investigator and others who have access to research records to refuse to disclose identifying information on research participation in any civil, criminal, administrative, legislative, or other proceeding, whether at the federal, state, or local level. By protecting researchers and institutions from being compelled to disclose information that would identify research participants, Certificates of Confidentiality help achieve the research objectives and promote participation in studies by helping assure confidentiality and privacy to participants.

10.1.4 FUTURE USE OF STORED SPECIMENS AND DATA

Data collected for this study will be analyzed and stored at the UNC HIV Cure Center. After the study is completed, the de-identified, archived data will be stored in the UNC Cure Center Database, for use by the UNC HIV Cure Center researchers. Permission to transmit data to researchers outside the UNC HIV Cure Center Collaboratory will require review and approval by the UNC IRB. In some circumstances, we will need to obtain additional consent from participants to share samples collected for the purpose of this study.

With the participant's approval and as approved by the UNC IRB, de-identified biological samples will be stored at the UNC HIV Cure Center and/or the UNC Chapel Hill HIV/STD Laboratory Core. These samples could be used to research the causes of HIV cure for which individuals with HIV infection can greatly benefit. The UNC HIV Cure Research Laboratories will also be provided with a code-link that will allow linking the biological specimens with the phenotypic data from each participant, maintaining the blinding of the identity of the participant.

During the conduct of the study, an individual participant can choose to withdraw consent to have biological specimens stored for future research. However, withdrawal of consent with regard to biosample storage may not be possible after the study is completed.

When the study is completed, access to study data and/or samples will be provided through the UNC HIV Cure Center Laboratory.

